
Summary of Study Design:
 
This is a Phase 2, parallel-group, long-term extension (LTE), dose-blind, global, multicenter study to evaluate the long-term safety and efficacy of AL002 in participants with Alzheimer’s disease (AD). The study will enroll participants who completed the planned treatment period in AL002-2 (parent study).
 
Objectives and Endpoints
 
The primary objectives of this Phase 2-LTE study (see Table 1) are to evaluate the long-term safety and tolerability of AL002 at 3 possible doses (ie, 15 mg/kg, 40 mg/kg, and 60 mg/kg) and to assess the effect of a slower dose titration on the incidence and severity of amyloid-related imaging abnormality (ARIA). The secondary objectives include the evaluation of pharmacokinetics (PK) of AL002 as well as clinical outcome assessments (COAs) in participants with AD. The exploratory objectives of this AL002-LTE study are to evaluate biomarkers and further assess the immunogenicity of AL002 in participants with AD.
 
Safety will be assessed through monitoring of adverse events (AEs) (including adverse events of special interest [AESIs] and serious adverse events [SAEs]), changes in laboratory and vital sign values, incidence of findings from physical, neurological, electrocardiogram (ECG), magnetic resonance imaging (MRI), ophthalmological examinations, and reports of suicidal ideation or behavior. Incidence and severity of ARIA will be assessed in participants undergoing titration. Participants’ serum PK will be assessed for investigation of exposure-response and exposure-safety relationships. Blood samples for assessment of anti-drug antibodies (ADA) will be taken throughout the study. Biomarkers will be assessed from fluid (blood/plasma, cerebrospinal fluid (CSF)), and imaging (MRI, optional tau positron emission tomography (PET) with tau radiotracer fluorine-18 MK-6240 ([F]MK-6240), and Amyloid PET). Longitudinal CSF, Tau PET and Amyloid PET will be assessed for all participants who consent to these optional assessments. Those who did not previously opt-in to these procedures in AL002-2 may choose to either opt-in or opt-out in this AL002-LTE study.
	

Investigational Plan

The first dose of the AL002-LTE study should be within the 4-week  $\pm$ 5-day window of the last dose of the parent study, to maintain continuity of study treatment. Delays of the first AL002-LTE dose beyond that window will constitute protocol deviations.

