## 2. OBJECTIVES AND ENDPOINTS

**Table 1: Study Objectives and Endpoints**

Primary Objectives	Primary Endpoints
To evaluate the long-term safety and tolerability of AL002 in participants with AD	
 
● Incidence of AEs, including AESIs and SAEs
 
● Vital signs, clinical laboratory results, and incidence of findings from physical, neurological, ophthalmological examinations, and ECG
 
● C-SSRS
 
● MRI abnormalities
 

To evaluate the effect of dose titration on ARIA	
 
● Incidence and severity of ARIA in participants undergoing titration
 

Secondary Objective	Secondary Endpoints
To evaluate the PK of AL002 in participants with AD	
 
● Serum PK concentrations of AL002 and relevant PK parameters
 

To evaluate the effects of AL002 on COAs in participants with AD	
 
● CDR®-SB
 
● MMSE
 
● RBANS-Update
 
● ADAS-Cog13
 
● ADCS-ADL-MCI
 
● ADCOMS
 

Exploratory Objectives	Exploratory Endpoints
To evaluate the effects of AL002 on biomarkers in participants with AD	
 
● Levels of sTREM2 in CSF and/or plasma
 
● Levels of biomarkers related to microglia function in CSF and/or plasma (eg, CSF1R, IL1RN, osteopontin, YKL 40)
 
● Levels of biomarkers related to AD pathology in CSF and/or plasma (eg, Aβ40, Aβ42, pTau, tTau)
 
● Levels of neurodegeneration biomarkers in plasma and/or CSF eg, NfL
 
● Brain volume, assessed by volumetric MRI
 
● Brain pathological tau burden as assessed by longitudinal Tau PET for participants who agree to participate in the optional assessment only
 
● Brain amyloid burden as assessed by longitudinal Amyloid PET scanning for participants who agree to participate in the optional assessment only
 

To evaluate immunogenicity of AL002 in participants with AD	
 
● Incidence of ADAs
 

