### 6.3.12. Magnetic Resonance Imaging

Safety will be assessed with structural brain MRI at screening/baseline and according to the visits outlined in the Schedule of Assessments (Table 9) to evaluate the presence of ARIA. An MRI must be done at least 5 days and not more than 10 days prior to dose escalation.

All new cases of ARIA-E and/or new cases of ARIA-H will require unscheduled MRI scans every 4 to 6 weeks until ARIA-E has resolved and/or ARIA-H has stabilized without new findings. An Amyloid PET scan may also be requested after the first occurrence of ARIA-E for those participants who have opted in to have longitudinal Amyloid PET performed.

Surveillance for treatment-emergent ARIA will be accomplished with post-baseline MRI scans as delineated in the Schedule of Assessments (Table 9).

If new or worsening ARIA is observed on any of these post-baseline MRIs, dosing should be managed as prescribed in the Dosing Guidelines for ARIA (see Table 8).

Participants with new or worsening radiographic evidence of ARIA on post-baseline MRI scans should be evaluated for neurological signs or symptoms during an unscheduled visit.

All MRIs will be read for brain abnormalities within 5 days by blinded independent radiologists at a central MRI reader with Brain MRI Worksheets (BMWs) provided to the clinical sites and Sponsor.

See Section 7.11 for a description of radiographic severity, resolution, and stabilization of ARIA findings, MRI surveillance for ARIA, and expectations for Investigator review of BMW reports. In addition to the MRI assessments prescribed in the Schedule of Assessments (Table 9) and in Section 7.11, the Sponsor may request that additional unscheduled MRIs be performed for the detection and follow-up of ARIA.

Specific information regarding the collection and processing of MRI images will be provided in a separate Imaging Procedures Manual.

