To maintain consistency of reporting across clinical sites, findings of ARIA-E or ARIA-H on MRI are determined by the MRI Central Reader by radiologists with expertise in assessing for ARIA and other abnormalities on brain MRI. ARIA-E, ARIA-H, and other findings are documented on and reported to the sites with the BMW report (see [Section 6.3.12](#)). The BMW provided by the central reader after each MRI examination scores ARIA-E (parenchymal vasogenic edema, leptomeningeal/sulcal effusion) according to: extent, location, number of sites involved, radiographic severity (mild, mild+, moderate, moderate+, severe), and changes since prior MRI exams. ARIA-E findings typically resolve radiographically and will be noted as such on the BMW of follow-up MRI scans. The BMW also documents occurrence and characteristics (location, size, number) of ARIA-H (parenchymal microhemorrhages and leptomeningeal hemosiderosis and macrohemorrhages). Radiographic severity of ARIA-H findings (“mild”, “moderate”, “severe”) is defined as follows for the 3 categories of ARIA-H ([Table 7](#)):

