2. STUDY OBJECTIVES AND ENDPOINTS

The study objectives and endpoints are provided in [Table 2-1](#).

Table 2-1. Study Objectives, Endpoints and Estimands for LTE

| Primary Objectives | Primary Safety Endpoints and Primary Estimand |
|--|---|
| 
To evaluate the long-term safety and tolerability of AL002 in participants with AD.
 | 
Part 1: Primary Safety Endpoint and Estimand:
 
 • Treatment condition: Group T-T (AL002 15 mg/kg, 40 mg/kg or 60 mg/kg IV Q4W) continues their Core Study treatment in the LTE Study; Group P-TC treated with Placebo in the Core study will be titrated to 60 mg/kg of AL002 in the LTE study. • Target population: adult participants with AD excluding apolipoprotein E (APOE) epsilon 4 (e4)-homozygous (e4/e4) participants. • Primary endpoints: AESI incidence and SAE incidence over all weeks. • Accounting for intercurrent events: a composite strategy will be used to handle intercurrent events as below: 
 ○ Hypothetical strategy for handling premature study drug discontinuation for any reason (AEs with a start date more than 90 days after study drug discontinuation are not counted) ○ Treatment policy strategy for handling all other intercurrent events. • Population-level summaries: the descriptive statistical summaries for each treatment group of incidence rates for all AESIs and SAEs over similar periods of time. 
Part 2: Primary Safety Endpoints:
 
 • Changes from baseline (CFBs) in vital signs, physical findings, neurological findings, ophthalmological findings, ECG findings, and clinical laboratory results. • MRI abnormalities (ARIA events) • C-SSRS. 
Primary Estimand for Safety Endpoints Above:
 
The estimand for the Part 2 endpoints is defined with similar attributes as for the Part 1 estimand except applied to the different endpoints
 |

| Primary Objectives | Primary Safety Endpoints and Primary Estimand |
|--|---|

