3. STUDY DESIGN

3.1 Study Design

This is a Phase 2, LTE study of participants with AD. The study will enroll participants who completed the planned treatment period in AL002-2 (Core Study). Study sites are located in North America, Australia, Europe, and Argentina.

Participants who were randomized to active treatment in the Core Study will remain on their previously assigned dose. Participants who were previously on placebo in the Core Study will be assigned to the Titration Cohort (TC), which will initiate with a starting dose of either 2 mg/kg or 6 mg/kg that will be increased over 32 weeks or 24 weeks, respectively, to reach the target dose of 60 mg/kg per the Titration Algorithm (for details of the Titration Algorithm, refer to the Study Protocol).

The planned duration of the LTE study is 56 weeks, and LTE study treatment extends from LTE Day 1 to Week 48. Dosing duration may be extended beyond this time through a protocol amendment, within the context of emerging favorable safety data. AL002 will be administered via IV infusion at the study site on Day 1 (after all necessary baseline assessments have been completed) and will be repeated subsequently once every 4 weeks throughout the treatment period.

The first dose of the AL002-LTE should be within the 4-week window (± 5 days) of the last dose of the Core Study, to maintain continuity of study treatment. Delays of the first AL002-LTE dose beyond that window will constitute protocol deviations.

Dosing for any individual participant may be stopped, paused, or reduced based on emerging safety data and/or the development of ARIA-E or ARIA-H. If a participant discontinues the study prior to the end of their planned treatment period, they will need to return for an Early Termination (ET) Visit and that will mark the end of their participation in the study.

At study entry and throughout the treatment period, safety will be assessed through monitoring of AEs (including AESIs and SAEs), changes in laboratory and vital sign values, incidence of findings from physical, neurological, ECG, MRI, ophthalmological exams, and reports of suicidal ideation or behavior. Serum PK will be assessed for investigation of exposure-response and exposure-safety relationships. Blood samples for assessment of ADA will be taken throughout the study.

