6.2.7 Magnetic Resonance Imaging (MRI) for Detection of ARIA-E and ARIA-H

A brain MRI will be performed to detect brain abnormalities, such as ARIA-E and ARIA-H.

For Integrated Analysis, definitions follow the definitions in the Core Study SAP. For LTE Analysis, definitions follow below. Note that these are restricted to events at or after the first AL002 dose in the LTE Study.

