All of the MRI summaries described above will also be provided separately for participants with the following APOE genotype(s) (1) e4 carriers (including e2/e4, e3/e4 and e4/e4), and (2) non-e4 carriers (excluding e2/e4, e3/e4 and e4/e4).

For Integrated Analysis, all summaries described in this section will be provided for events across two studies as defined in Section 7.4.1.2. For LTE Analysis, only the overall summary of ARIA will be provided for events during the LTE Study.

For Integrated Analysis, the difference in proportion of participants with ARIA-E events between a slower titration rate over 48 weeks and a faster titration rate over 48 weeks will be estimated by the Cochran-Mantel-Haenszel (CMH) method adjusting for the APOE e4 status. The faster titration rate will be represented by data from the AL002 60 mg/kg treatment group during the first 48 weeks of the Core Study among participants who were on dose titration (i.e., received the first dose on or after July 22, 2021 in the Core Study) and had at least one evaluable post-baseline MRI scan. The slower titration rate will be represented by data from the first 48 weeks of the LTE Study, among Titration Cohort participants who had at least one evaluable post-baseline MRI scan in the LTE Study. Both 90% and 95% CIs for the difference in the ARIA-E events and p-value will be reported from the CMH method. The same analysis will be repeated for ARIA-H.

The statistical tests (the CMH method) of ARIA events between the slower and faster titration groups will not be performed at the first IA at the time of unblinding of the Core Study due to limited data from the LTE study at this IA, but will be performed in all analyses after the first IA.

In the Integrated Analysis, the Kaplan-Meier curves for the time to the first occurrence of ARIA-E during both the Core and LTE Studies will be plotted. For participants who experienced at least one ARIA-E, the time to the first occurrence of ARIA-E is the time from the first dose date to the onset date of the first ARIA-E occurrence. For participants who did not experience ARIA-E, the censor date will be the earlier date of the last MRI scan date, any death date, and the last dose date plus 90 days. Similarly, the Kaplan-Meier curves for the time to the first occurrence of ARIA-H will be plotted.

All MRI findings will be listed.

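### SAP Table 2-1 narrows the primary MRI safety endpoint to ARIA; other centrally read abnormalities are only listed unless reported as adverse events

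*SAP*

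**What the plan says.** Protocol Table 1 lists "MRI abnormalities" under the long-term safety objective. ARIA in titrating participants is a separate endpoint under a separate objective. The synopsis says safety will be assessed through "incidence of findings from physical, neurological, electrocardiogram (ECG), magnetic resonance imaging (MRI), ophthalmological examinations", among other measures.

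On data collection, Protocol 6.3.12 states: "All MRIs will be read for brain abnormalities within 5 days by blinded independent radiologists". Protocol 7.11 adds: "ARIA-E, ARIA-H, and other findings are documented on and reported to the sites with the BMW report".

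The SAP is not uniform. Table 2-1 (Part 2) gives the endpoint as "MRI abnormalities (ARIA events". Section 3.1 still speaks of "incidence of findings from physical, neurological, ECG, MRI, ophthalmological exams", Section 6.2 lists MRI abnormalities among the safety variables without a limit, and Section 6.2.7 opens: "A brain MRI will be performed to detect brain abnormalities, such as ARIA-E and ARIA-H". The analysis section, 7.4.8, is confined to ARIA-E and ARIA-H apart from its last line: "All MRI findings will be listed". SAP Section 1 gives the SAP precedence where it differs from the protocol.

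**The concern.** A primary endpoint has changed scope between protocol and SAP without explanation, and the narrower scope drives the outputs.

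What drops out is the part that made the endpoint distinct. ARIA-E and ARIA-H are already adverse events of special interest (SAP 6.2.2.2), so Part 1 of Table 2-1 counts them in every group, and Part 3 covers them under titration. Restricted to ARIA, the Part 2 MRI item largely repeats those two. Non-ARIA findings are what the protocol's broader endpoint adds.

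Protocol 7.11 also leaves open whether MRI findings caused by AL002 are related to amyloid, and uses the term ARIA provisionally until the mechanism is better understood. A primary MRI endpoint limited to that category cannot show whether other abnormalities emerged more often in one group than in another.

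**Working it through.** No arithmetic applies, because the point concerns endpoint scope. The check compares the stated endpoint with the planned outputs.

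1. **Scope of the endpoint.** Unrestricted: Protocol synopsis, Protocol Table 1, SAP 3.1, SAP 6.2. ARIA as an example only: SAP 6.2.7. Restricted to ARIA: SAP Table 2-1. No rationale for the restriction appears in the SAP text available.

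2. **Data available.** All scans go to a blinded central reader (Protocol 6.3.12). The BMW carries other findings as well as ARIA (Protocol 7.11). The raw material for the unrestricted endpoint is therefore collected.

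3. **Planned MRI outputs.** SAP 7.4.8 plans incidence by radiographic severity, time to first occurrence, breakdown by APOE genotype, the Cochran-Mantel-Haenszel comparison of titration rates and Kaplan-Meier curves for ARIA-E and ARIA-H. Resolution and recurrence are planned for ARIA-E. The LTE Analysis has only the overall ARIA summary. The first interim analysis (SAP 8.1.3) has only the ARIA summaries. The count for non-ARIA central findings is:

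| Analysis | Incidence tables |
|---|---|
| Integrated Analysis | 0 |
| LTE Analysis | 0 |
| First interim analysis | 0 |

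Against this stands one by-participant listing of all MRI findings.

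4. **Indirect route.** Protocol 7.6.1 makes an imaging finding an adverse event if it is confirmed and the Investigator considers it clinically significant, if it requires discontinuation, or if it requires treatment. Such a finding is then counted, as number and percentage by treatment group, in the treatment-emergent adverse event tables of SAP 7.4.3. This route counts a different event: the Investigator's judgement decides, not the central read.

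5. **Volumetric MRI.** SAP 7.7 analyses regional brain volumes as biomarkers. That is not an incidence of abnormalities.

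The centrally read non-ARIA part of the endpoint is thus collected and listed, but not summarised by group.

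**The case against.** The strongest reply is that the safety MRI exists to look for ARIA. Protocol 6.3.12 opens with that purpose, and Protocol 7.11.1 describes the scans as ARIA surveillance, so the parenthesis in Table 2-1 may only state what was meant. This explains the emphasis. It does not rewrite Protocol Table 1, which lists MRI abnormalities apart from the ARIA titration endpoint.

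A second reply is that important findings are counted anyway. Investigators are told to review the BMW for ARIA or other abnormalities (Protocol 7.11.2), and to report when in doubt (Protocol 7). This stands in part. A reader might infer that non-ARIA findings have no incidence estimate of any kind, or that a new infarct would appear in no SAP table. The documents do not support either inference: a finding that meets the adverse event criteria is tabulated by group. What remains untabulated is the central read itself, including findings that the Investigator does not report.

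Third, SAP 7.4 says all safety endpoints are summarised in the Integrated Analysis unless otherwise specified, and SAP 7.1 makes counts and percentages the default for categorical variables. These general rules name no non-ARIA summary, and under the Table 2-1 wording they would have only ARIA to act on.

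Fourth, the protocol's own safety analysis text (8.3.3) is partly blacked out, and the protocol leaves methods to the SAP. Nothing is inferred here from the redaction; the point rests on the visible endpoint wording.

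Fifth, Protocol 7.11 specifies the scoring of ARIA-E and ARIA-H but gives no categories or coding for other findings. This stands, and it limits how detailed a table can be promised.

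**Conclusion.** The point holds as a mismatch of scope. Table 2-1 restricts a primary safety endpoint that the protocol and three other SAP sections leave unrestricted, and the planned MRI tables follow the restriction. The endpoint is descriptive, so no hypothesis test is affected. The loss is one of reporting: a primary endpoint would be only partly summarised although the central reads exist.

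Its size is the count above: no incidence table against one listing. The documents give no background rate of non-ARIA findings, so any figure for participants affected, or for the precision of an estimate, would rest on an invented rate; none is offered.

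A reader might also infer from the MRI exclusion criteria in Protocol 4.2 that the BMW records infarcts and white matter lesions after baseline as coded categories. The documents do not show this.

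The conclusion assumes only that the BMW records other findings, as Protocol 7.11 says, and that no summary of them is planned in a document outside those supplied.

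**What to change.** In SAP Table 2-1, restore the unrestricted endpoint so that it agrees with Sections 3.1, 6.2 and 6.2.7.

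In SAP 7.4.8, add one descriptive table from existing BMW data: number and percentage of participants with any post-baseline non-ARIA finding not present on the baseline scan, by treatment group. Use the baselines already set in SAP 7.4: Core baseline for placebo and Group T-T, LTE baseline for the Titration Cohort. Break the table down by category only as far as the BMW records categories.

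The cost is the wording change, modest programming and, if the BMW holds other findings as free text, some coding of those entries. No additional scans are required.
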